5.1 Description

Patients will be randomized (1:1) to receive either systemic therapy/observation (Arm A) or early RT plus systemic therapy / observation (Arm B).

Arm A:

The observational arm (Arm A) will include **observation or systemic therapy**, according to the treating physician's discretion. Systemic therapy may include continuation of the current systemic therapy or initiation of a new systemic therapy.

These patients will be able to receive palliative RT to progressed, painful lesions (an SSE) only at the time of symptom worsening (NRS > 2/10 or need for opioids) or determination of spinal cord compression with neurological symptoms or (high risk for) fracture requiring surgical intervention. Upfront preventive RT is not allowed.

Arm B:

The intervention in this study is **early, upfront radiation therapy** to asymptomatic or minimally symptomatic (defined as high-risk) bone metastases. Up to 5 high-risk asymptomatic or minimally symptomatic metastatic locations per patient are allowed.

The radiotherapy (RT) doses used will be in accordance with common practice palliative RT schedules. As such a single fraction of 8 Gy is considered for all patients, except for patients with a very good prognosis (NRF prognostic score 0-1) in which a higher dose will be used with SABR [Chow et al].

Table 3: Predictive model for estimation of median overall survival (OS): NRF-model [Chow et al].

Three variables:

- **Primary cancer type** -> risk factor: non breast/prostate/lung cancer
- **Site of metastases** -> risk factor: metastases other than bone
- **Karnofsky performance score (KPS)** -> risk factor: KPS ≤60

0-1 risk factors	median OS 64 weeks	95%CI: 37-undefined
2 risk factors	median OS 28 weeks	95% CI 22-34
3 risk factors	median OS 10 weeks	95% CI 8-13

Simulation:

All patients will be immobilized in a comfortable and stable position to irradiate the metastatic lesion(s). Support and/or immobilization devices will be used to increase patient comfort or to ensure set-up reproducibility. A planning CT scan will be acquired without intravenous contrast with <3mm CT slice thickness (1mm for SABR) encompassing the region of interest with sufficient margin for treatment planning, a typical scan length should extend at least 10 cm superior and inferior beyond the treatment field borders. The isocenter will be placed in the middle of the affected bone lesion.

Target volume definition:

1. *Conventional radiotherapy:*

The Gross Tumor Volume (GTV) will consist of the metastatic lesion(s) as visualized on CT. All available diagnostic imaging (PET-CT, MRI) will be used in order to delineate the target structures as accurate as possible.

A Clinical Target Volume (CTV) is delineated using a 5 to 10 mm margin on the GTV respecting the anatomical boundaries.

For spinal lesions, delineation of the whole affected vertebra is recommended as CTV.

The Planning Target Volume (PTV) will be created by using a 3-dimensional margin on the CTV to allow for daily set-up variance and organ motion. Margins depend on the radiation technique ranging from 5 up to 10 mm for 3D conformal low dose radiation.

Organs at risk (OAR) within 10 cm of the target volume will be contoured as visualized on the planning CT depending on the localization of the target lesion.

2. SABR:

The Gross Tumor Volume (GTV) will consist of the metastatic lesion(s) as visualized on CT. All available diagnostic imaging (PET-CT, MRI) will be used in order to delineate the target structures as accurate as possible.

For spinal lesions an MRI in treatment position is mandatory.

A Clinical Target Volume (CTV) is delineated using a 5 to 20 mm margin on the GTV respecting the anatomical boundaries [Nguyen et al].

For spinal lesions, delineation of the whole affected vertebra is recommended as CTV.

The Planning Target Volume (PTV) will be created by using a 3-dimensional margin on the CTV to allow for daily set-up variance and organ motion. Margins depend on the radiation technique ranging from 2-5 mm margins for bony lesions treated with SABR. For spinal lesions, a PTV_high is created around the GTV and a PTV_low around the CTV respectively.

Organs at risk (OAR) within 10 cm of the target volume will be contoured as visualized on the planning CT depending on the localization of the target lesion. In case of SABR, a Planning Organ at Risk Volume (PRV) expansion will be added to the OAR for setup uncertainty or organ motion and all dose constraints apply for this PRV.

Bone metastases that are within 5 cm of each other will be treated as one site.

Treatment planning:

1. Conventional radiotherapy:

Standard fractionation will be 1x8 Gy. Although there is evidence in current literature that a single dose of 8 Gy is non-inferior in terms of pain control, there is no evidence for the current trial endpoint (development of SSE) so other fractionation regimens (e.g. 20 Gy in 5 fractions or 30 Gy in 10 fractions) are accepted and decided by the treated physician.

To minimize treatment time, the preferred treatment planning is rotational intensity-modulated radiation therapy (IMRT), i.e., volumetric modulated arc therapy (VMAT), using 6-MV photons. Conformal 3D-RT is also allowed in case of standard dose. Prescribing, recording and reporting of the doses will be consistent with the recommendations in Report 91 of the International Commission on Radiation Units and Measurements (ICRU) [ICRU et al].

In the standard setting, 95% of the PTV should receive 95% of the prescribed dose while near maximum dose (Dnear-max) in the PTV should not exceed 107%.

2. SABR:

For patients with a better prognostic outcome (NRF score 0-1) a higher dose will be delivered with SABR using either 1x20 Gy, 2x12 Gy, 3x10 Gy or 5x8 Gy (schedule will depend on the coverage and dose to OAR during treatment planning). However, dose can be changed towards a palliative dose when SABR is not expected to be safe (for example in case of high-risk bone lesions such as impending bone fracture).

For spinal lesions, a simultaneous integrated boost (SIB) planning will be used, where the high-dose PTV receives a higher dose in regard to the non-affected bone included in the low-dose PTV. SABR using a SIB technique will be delivered in 2 fractions of 12 Gy to the PTV_high and 2 fractions of 6 Gy to the PTV_low.

To minimize treatment time, the preferred treatment planning is rotational intensity-modulated radiation therapy (IMRT), i.e., volumetric modulated arc therapy (VMAT), using 6-MV photons. Conformal 3D-RT is also allowed in case of standard dose. Prescribing, recording and reporting of the doses will be consistent with the recommendations in Report 91 of the International Commission on Radiation Units and Measurements (ICRU) [ICRU et al].

In the SABR arm, the planning aim is to have 99% of the PTV receiving the prescription dose for an optimal target coverage. Because no violation of the OAR constraints nearby is allowed, covering of 90% (or at least 80%) is allowed to receive the prescribed dose. If this is not possible, an adaptation of the fractionation regimen is necessary towards a more fractionated treatment (radiobiological better than a decreased dose). Covering <80% will be reported as a minor protocol deviation.

Maximum PTV dose up to 140% is allowed but all dose > 105% should be contained within the PTV and preferably within the GTV. A dose fall-off outside the PTV extending into normal tissue structures should aim at 50% of the prescribed dose within 3 cm.

The OAR dose constraints for SABR will be in accordance with the recommendations from the report of the UK [Diez et al]. If a dose constraint cannot be achieved due to overlap of the target with an OAR, the target coverage can be compromised in order to meet the constraint.

Treatment delivery:

All treatments will be performed with high-precision image guided RT using a linear accelerator with ESTRO-ACROP specifications for SABR [Freisleder et al].

1. Conventional radiotherapy:

In the conventional RT group, image-guidance will consist of portal images or cone-beam CT showing the relevant bony anatomy.

2. SABR

In the SABR arm, a cone-beam CT will be performed for image guidance and positioning will be adapted using a 3 or 6 degrees of freedom treatment couch.

5.2 Allocation to treatment groups and blinding

This is a randomized controlled trial. Due to the type of intervention, blinding is not possible.

Randomization will be completed on a per patient basis (not lesion based) in a 1:1 ratio to the observational arm receiving systemic therapy / observation (Arm A) or to the arm receiving early RT plus systemic therapy / observation (Arm B). Randomization will be performed by the site staff in the window between screening and start of treatment using an electronic randomization tool in the eCRF that uses variable block randomization as randomization algorithm.

The following stratification factors are taken into consideration for randomization:

- NRF prognostic class (0-1 vs 2)
- high-risk disease location (spine location vs. other)
- bone modifying agents (yes vs. no).

Assignment of the subject identification number

At screening, each potential study participant will be assigned a subject identification number that will be retained as the primary identifier for the subject throughout their participation in the study. The subject-id consists of a sequential 6-digit number (comprised of a 2-digit study site number -11, 12, etc.- and a 4-digit number incremental per center representing the sequential order in which they are screened: 110001, 110002, etc.), so that each subject is numbered uniquely across the entire database. Upon signing the ICF, the subject is assigned to the next sequential subject-id available to the Investigator through the electronic data capture system.

5.3 Treatment compliance and adherence

After the RT session(s), RT parameters should be captured in the eCRF. The study site must maintain accurate records demonstrating dates and details of treatment interventions of all patients that have entered the study and capture these in the eCRF.

The following RT parameters are collected at the end of the RT treatment:

- radiation technique used
- date of the first and last RT session
- total dose delivered
- number of fractions delivered
- if early termination of RT, reason for this as well as fractions and dose that were originally planned
- GTV Volume: ... cm³

- PTV: V100% = ...%

Furthermore, at the end of the treatment period it will be documented in the eCRF whether the patient received observation or systemic therapy. In case systemic therapy was used, the following information will be recorded:

- Name of systemic therapy
- Start date systemic therapy
- Whether systemic therapy was interrupted for RT (and if applicable the duration of the interruption)

5.4 Prohibited or restricted medications/interventions

There are no prohibited medications.

All pain medication (including corticoid therapy), bone-modifying agents and anticancer therapy used within 7 days prior to the screening visit and through the end of the study will be recorded.

The decision for (dis)continuation of concomitant anticancer therapy with possible radiosensitizing effects is left at the discretion of the treating physician.

6. Study conduct

6.1 Study procedures

As noted in Section 3.1, participation in the HERMES study will comprise a screening period, where screening assessments must be completed. Eligible, consenting subjects will then undergo treatment with a post-treatment follow-up period to monitor safety and efficacy. The visit schedule and all study procedures and assessments are presented in the SOE in Table 1.

The results of all assessments and procedures will be documented in the subject's medical record and in study documentation, including the electronic case report form (eCRF), as applicable.

6.1.1 Screening period

Documentation of written informed consent (from the patient or his/her legally authorized representative) is required before any study specific procedure, including screening procedures, takes place.

Patients will be screened for eligibility (i.e. fulfilling inclusion/exclusion requirements) based on medical record, anamnestic and clinical information from the treating physician.

Screening will include the following evaluations:

- Demographic data (see section 7.1.2.)

- Medical history and prior medications (i.e. anticancer therapy, bone-modifying agents and pain medications (including corticoid therapy) taken within 7 days prior to screening) (see section 4.4.3. and section 7.1.1.).
- Determination of Karnofsky performance score (KPS) (see section 7.1.4 and appendix 5.)
- Pain assessment (NRS score; see section 7.1.3. and appendix 1)
- Determination of high-risk metastase(s) characteristics (see section 7.1.5.)
- Quality of life questionnaires (see section 7.1.6. and section 7.4)
- Pregnancy test in case of premenopausal women (see section 7.1.7. and section 4.4.1.)
- Reporting of adverse events that are related to the bone metastatic disease or related to the radiotherapy (only for patient in arm B) as measured with NCI-CTCAE v5.0 (see appendix 4)

More details regarding screening assessments can be found in section 7.1. Once all screening procedures are completed, eligibility will be determined according to the inclusion/exclusion criteria as detailed in section 4. The review of eligibility criteria must be captured in the eCRF.

6.1.2 Treatment planning and treatment period

Upon enrollment in the study, patients will be randomized into either the observational arm receiving observation / systemic therapy (arm A) or the upfront RT arm receiving upfront RT plus systemic therapy / observation (arm B).

For patients randomized in arm B, radiotherapy will start within 21 days after the date of randomization. Treatment planning and delivery is described in section 5.1.

Any toxicity (graded according to CTCAE v5.0) that occurs during this period should be entered in the database. AE that took place during this treatment period will be documented at the first follow-up visit.

6.1.3. Follow-up period

During on site follow-up visits at 1 month (+/-1 week), 3 months (+/- 3 weeks), 6 months (+/- 3 weeks), 12 months (+/- 3 weeks), 18 months (+/- 3 weeks) and 24 months (+/- 3 weeks) after date of randomization, the following assessments will take place:

- Determination of Karnofsky performance score (KPS) (see appendix 5)
- EQ-5D-5L QoL and QLQ-C15-PAL questionnaire (see appendix 2, appendix 3 and section 7.4)
- Acute and late toxicity assessment: as measured with NCI-CTCAE v5.0 (see appendix 4)
- Concomitant medications: pain medication (including corticoid therapy), bone-modifying agents and anticancer therapy (see section 4.4.3.)
- Survival data (survival status, date of death, primary cause of death)

Follow-up imaging will not occur standardized but is left at the discretion of the treating physicians (i.e. is part of the standard of care).

6.2 End of study

The end of the study is defined as the date when the last follow-up visit takes place (i.e. 24 months after date of randomization of the last participant if his/her participation was not discontinued early)

In case an SSE occurs, the assessments that should take place during the next follow-up visit, should be completed at that time point, preferentially within one week. These assessments must be documented in the eCRF. Furthermore, the type of SSE (e.g. symptomatic pathological fracture,...) needs to be registered. In case of fracture or compression, the location and planned treatment must also be documented. In case of RT or surgery, the location and reason must be registered. Afterwards, only survival data and possible occurrence of another SSE will be recorded on the planned FU visits until 24m after the randomization date.

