- e. Health related quality of life parameters will be reported by subjects using the EORTC QLQ-C15-PAL and EQ-5D-5L questionnaires
- f. All pain -and anticancer medications (including corticoid therapy) and bone-modifying agents used during the study will be recorded. The dates of administration, method of administration, dosage, and reason for use will be included.
- g. A month can be 28, 29, 30 or 31 days, depending on the month.
- h. Occurrence of an SSE during the study should be reported to the study team immediately. In case an SSE occurs, the assessments that should take place during the next follow-up visit, should be completed at that time point, preferentially within one week. These assessments must be documented in the eCRF. Furthermore, the type of SSE (e.g. symptomatic pathological fracture,...) needs to be registered. In case of fracture or compression, the location and planned treatment must also be documented. In case of RT or surgery, the location and reason must be registered. Afterwards, only survival data will be recorded on the date of the planned FU visits until 24m after the randomization date as well as possible occurrence of another SSE within 24m after the randomization date.

Clinical Trials Oncology

Ref.Nr.: P.01-S.23

Versie: 6.0

- i. During the study (from time of study randomization to date of death of any cause or last follow-up visit (24m after randomization date) or early end of participation in the study due to other reasons), hospitalizations related to the high-risk bone metastase(s) should be documented in the eCRF. More specifically, the hospital admission date and date of discharge will be recorded as well as whether the hospitalization is related to an SSE (if yes, it should be specified to which SSE).

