8.2.2 Period for collecting AE and SAE information

During the period from main ICF signing to the last follow-up visit (24m after randomization date), date of death of any cause or early end of participation in the study due to other reasons, all (S)AE that are related to the bone metastatic disease or related to radiotherapy (only applicable for patients in arm B) will be documented in both study arms.

The following applies for (S)AE related to RT (arm B):

Toxicity that appears within 90 days after the last RT dose will be regarded as acute toxicity.

Toxicity that appears >90 days after the last RT dose administration will be regarded as late toxicity.

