9.3 Statistical methods for analysing primary and secondary outcomes

Primary objective:

The primary endpoint (SSE-free survival) is a composite endpoint of SSEs and death (death before SSE is part of the endpoint, not a competing risk). The primary endpoint is time until the occurrence of SSE in any bone metastasis or death from the date of randomization whichever occurs first. Data suggest that the median SSE-free survival is around 10.4 months. With a HR of 0.5, we hypothesize that the median SSE-free survival will be 20.8 months.

A proportion of patients will have multiple high-risk bone lesions. Pain will be reported lesion-based, however the SSE-free survival remains patient-based as this is more clinically relevant.

Secondary objectives

- The number of **hospitalizations** related to the high-risk metastase(s) will be compared between systemic therapy / observation (arm A) and upfront RT plus systemic therapy / observation (arm B) from date of study randomization to last follow-up visit (24m after randomization date), date of death of any cause or early end of participation in the study due to other reasons
- **Overall survival** will be assessed from time of study randomization to date of death of any cause or last follow-up visit (24m after randomization date)
- **Quality of life** will be compared between systemic therapy / observation (arm A) and upfront RT plus systemic therapy / observation (arm B), using the EORTC QLQ-C15-PAL questionnaire (see appendix 2) and the EuroQol Group EQ-5D-5L questionnaire (see appendix 3)
- **Adverse events** in both study arms will be evaluated using the National Cancer Institute Common Terminology Criteria for Adverse Events (NCI-CTCAE) v5.0 (see appendix 4) from the time of ICF signing to last follow-up visit (24m after randomization date), date of death of any cause or early end of participation in the study due to other reasons. Only adverse events that are related to the bone metastatic disease or related to the radiotherapy (only for patients in arm B) will be reported in the eCRF.

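### Quality-of-life collection ends at the first SSE, an outcome the treatment is meant to change, and the same rule contradicts the 24-month windows for hospitalisations and adverse events

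*Protocol*

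**What the plan says.** **The rule.** Section 6.2 states that when an SSE occurs, "the assessments that should take place during the next follow-up visit, should be completed at that time point, preferentially within one week". It continues: "Afterwards, only survival data and possible occurrence of another SSE will be recorded on the planned FU visits until 24m after the randomization date". Footnote h to Table 1 gives the same rule: "Afterwards, only survival data will be recorded on the date of the planned FU visits until 24m after the randomization date", together with any further SSE. By section 6.1.3, a full follow-up visit comprises Karnofsky score, both questionnaires, toxicity, concomitant medication and survival.

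**Quality of life.** Section 9.3 says it "will be compared between systemic therapy / observation (arm A) and upfront RT plus systemic therapy / observation (arm B), using the EORTC QLQ-C15-PAL" and the EQ-5D-5L. No collection window is stated, and no passage continues the questionnaires after an SSE.

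**Hospitalisations.** Footnote i says that, from randomisation to death, 24 months or early end of participation, "hospitalizations related to the high-risk bone metastase(s) should be documented in the eCRF". It also asks "whether the hospitalization is related to an SSE (if yes, it should be specified to which SSE". Section 9.3 gives the window as "from date of study randomization to last follow-up visit (24m after randomization date), date of death of any cause or early end of participation". The synopsis and Table 2 agree.

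**Adverse events.** Section 8.2.2 sets the period as "During the period from main ICF signing to the last follow-up visit (24m after randomization date), date of death of any cause"; leaving the study early also ends it. The synopsis, Table 2 and section 9.3 match it. None of these windows ends at an SSE, and section 6.3.1 does not name an SSE among the reasons for early termination.

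**The concern.** Section 1 says that SSEs impair quality of life, that this often cannot be fully restored, and that early radiotherapy is expected to help by reducing SSEs. The period after an SSE is therefore where a quality-of-life benefit should show, and for the questionnaires that period is not observed. Collection ends because of a post-randomisation outcome that the treatment is meant to affect, so the missing data are informative. No analysis plan can recover answers that were never collected. It could only impute them on assumptions that cannot be tested.

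The stopping event may also be fairly mild. An SSE includes an indication for palliative radiotherapy, which section 5.1 opens in arm A once the NRS exceeds 2 or opioids are needed.

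For hospitalisations and adverse events, two sites could both claim compliance while recording different things. A site that follows section 6.2 would leave out later bone-related admissions and adverse events. In arm B that includes late radiotherapy toxicity in patients whose SSE may lie in an unirradiated bone. A site that follows footnote i and section 8.2.2 would record them.

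**Working it through.** **Inputs.** Section 9.1: 2-year SSE-free survival 20% (arm A) and 45% (arm B), hazard ratio 0.5, exponential times, alpha 0.05, power 0.8, dropout 20%, 65 events, 96 patients, 120 with dropout. Section 9.3: medians 10.4 and 20.8 months; the endpoint is SSE or death. Allocation is 1:1, so 60 per arm. The share of first events that are SSEs is not given.

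**1. The plan's own figures reproduce.**
- Events (Schoenfeld, two-sided 0.05): 4 × (1.960 + 0.842)² / (ln 0.5)² = 65.3, against 65 stated.
- Arm B at 24 months: 0.20^0.5 = 0.447, the stated 45%.
- Patients: mean event probability (0.800 + 0.553)/2 = 0.676; 65/0.676 = 96.1; 96/0.8 = 120.
- Hazard in arm A: λ = −ln(0.20)/24 = 0.0671 per month, giving medians of 10.3 and 20.7 months, against 10.4 and 20.8 stated.

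**2. Share still free of SSE and death**, S(t) = exp(−λt) in arm A and exp(−λt/2) in arm B:

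| Month | Arm A | Arm B | Of 60: A vs B |
|---|---|---|---|
| 6 | 67% | 82% | 40 vs 49 |
| 12 | 45% | 67% | 27 vs 40 |
| 18 | 30% | 55% | 18 vs 33 |
| 24 | 20% | 45% | 12 vs 27 |

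Mean event-free time to 24 months is (1 − 0.200)/0.0671 = 11.9 months in arm A and (1 − 0.447)/0.0335 = 16.5 months in arm B. These figures include deaths, which end questionnaires under any rule, and they ignore dropout.

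**3. Share cut off by an SSE rather than by death.** Let f be the SSE share of first events, taken as equal in both arms. By 24 months the rule removes f × 0.800 of arm A and f × 0.553 of arm B:

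| Assumed f | Arm A | Arm B | Of 60: A vs B |
|---|---|---|---|
| 25% | 20% | 14% | 12 vs 8 |
| 50% | 40% | 28% | 24 vs 17 |
| 75% | 60% | 41% | 36 vs 25 |
| 100% | 80% | 55% | 48 vs 33 |

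**4. Sensitivity to the effect.** With hazard ratio 0.7 and f = 100%, arm B is 1 − 0.20^0.7 = 68%, against 80% in arm A. With hazard ratio 1 the expected loss is the same in both arms, but quality of life after an SSE is still missing in each.

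**5. The passages side by side.** Section 6.2 and footnote h allow only survival and further SSEs after the first SSE. Footnote i, section 8.2.2, Table 2, the synopsis and section 9.3 require hospitalisations and adverse events to 24 months, death or early end. Read literally, both cannot be followed.

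**The case against.** A reader might infer that hospitalisation and toxicity data simply stop at the first SSE. The documents do not support that. Their windows do not end there, and footnote i, by asking to which SSE an admission belongs, implies that admissions are recorded after SSEs. Section 6.2 restricts what is recorded at planned visits, and hospitalisation is not in the visit list of section 6.1.3. Section 8.2.3 separately requires SAEs to be reported within 24 hours. It is reasonable to read footnote i and SAE reporting as surviving the rule. Non-serious adverse events, asked about at visits, remain ambiguous. For these outcomes the defect is a contradiction, and bias follows only if sites obey section 6.2.

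A reader might also infer that quality of life is compared among event-free survivors only. That is wrong, because the assessment at the SSE includes both questionnaires. It gives one measurement near the event, replacing the next scheduled one, and shows neither lasting loss nor recovery.

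Thirdly, 45% versus 67% is not the size of the defect. Table 3 gives a median survival of 64 weeks for NRF 0-1 and 28 weeks for NRF 2. If survival is exponential, 2^(−52/64) = 57% and 2^(−52/28) = 28% are alive at 12 months. Even with every patient in NRF 0-1, the recoverable loss in arm A at 12 months would be about 57% − 45% = 12 points, or 7 of 60. Better survival than Table 3 would raise this. Arm B's 67% already exceeds the Table 3 survival, so the protocol's figures cannot isolate the part due to SSEs. This objection stands, and it is why step 3 shows a range.

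Finally, the missing answers are probably the worse ones and more of them fall in arm A. The bias would then probably flatter arm A and work against the radiotherapy claim. That is plausible but cannot be proved from the protocol.

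**Conclusion.** The point holds in two parts. For quality of life the flaw is real: both passages that govern follow-up after an SSE end the questionnaires after one assessment, and no other passage restores them. For hospitalisations and adverse events the protocol contradicts itself, and loss of data depends on which passage sites follow.

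By 24 months the rule would cut off 20% to 80% of arm A and 14% to 55% of arm B. This assumes exponential times, hazard ratio 0.5, and an SSE share of first events of 25% to 100%, equal in both arms. The difference between arms is an expectation under the trial's hypothesis, not something the protocol states. The size and direction of the quality-of-life bias cannot be determined from the document. Primary endpoint, overall survival and further SSEs continue to be recorded to 24 months.

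**What to change.** Amend section 6.2 and footnote h to state that, after an SSE, QLQ-C15-PAL, EQ-5D-5L, adverse events and hospitalisations continue to be collected until 24 months, death, withdrawal of consent or early end of participation. Keep the assessment at the SSE as an additional time point, not a replacement for the next visit. Align the wording with footnote i and section 8.2.2.

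If the sponsor prefers to stop collection, the alternative is to redefine these endpoints as running to the first SSE and to change Table 2, the synopsis, footnote i, section 8.2.2 and section 9.3 to match. That removes the contradiction but gives up the quality-of-life course after an SSE.

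The cost is a protocol amendment and some extra questionnaires for sicker patients. Survival and SSE status are already recorded at the planned visit dates. The protocol does not say that these patients still attend on site, so some added visits or remote contacts may be needed.
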